#### *Part B*

The analysis of exploratory endpoints for Part B will be performed using the **FAS – Part B**. The methods of analyses of exploratory endpoints for Part B will be the same as the analysis of exploratory endpoints for Part A. In addition, Bayesian methods may be used to borrow historical control data in estimating treatment effect, in addition to using observed data from the current study.

The time to achieving EASI 50/75/90 response prior to switching to tezepelumab 420 mg Q2W will be summarized by Kaplan-Meier (KM) curves, the number of subjects achieving EASI 50/75/90 and the number of subjects censored will be provided at available time points. Subjects who do not achieve EASI 50/75/90 will be censored at the date when formal assessments of non-responder (as defined in protocol, that is, not achieve at least 50% improvement in EASI at week 16 compared to baseline) are recorded or end of study date, whichever is the earliest. Subjects who receive rescue medication from day 29 will be censored at the point when subjects receive rescue medication.

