Part A is a dose-ranging, randomized, placebo-controlled, double-blind study designed to evaluate the safety and efficacy of tezepelumab as monotherapy in subjects with moderate-to-severe AD. Following the screening period, eligible subjects will be randomized 1:1:1:1 to receive 420 mg SC Q2W, 280 mg SC Q2W, 210 mg SC Q4W, or placebo. All subjects will receive a 420 mg SC dose (investigational product or placebo) as the first dose. Subjects will then receive the appropriate dose of investigational product at the week 2 visit, depending on which treatment group they are randomized to. Depending on if they are randomized to Q2W or Q4W dosing, the dose at week 2 could be placebo or tezepelumab. Non-responders are defined as those subjects who have not achieved at least a 50% improvement in EASI at week 16 compared to baseline (day 1). Subjects who are determined to be non-responders in Part A will receive tezepelumab 420 mg SC Q2W for the remainder of the study, beginning with the

week 18 dose. The randomized treatment assignments for the non-responders will remain blinded until the end of study.

Part B is a randomized, placebo-controlled, double-blind study designed to evaluate the safety and efficacy of tezepelumab when administered with moderate class TCS in adults with moderate-to-severe AD. Enrollment of subjects in Part B of the study will only commence if there is a result of “not futile” for the first interim analysis in Part A and Part A has completed enrollment of 240 patients. Following the screening period, eligible subjects will be randomized 2:1 to receive 420 mg SC Q2W or placebo; both groups in Part B will be allowed to use TCS after the day 1 visit. Non-responders in Part B will not be switched to 420 mg SC Q2W at week 18 and will remain on their initial dose for the duration of the study.

The overall study design is described by a study schema in [Section 2.1](#). The endpoints are defined in [Section 4.1](#).

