7.4 Dose Modification

In Part A of this study, subjects who are determined to be non-responders will receive tezepelumab 420 mg SC Q2W for the remainder of the study, beginning with the week 18 dose. Non-responders are defined as those subjects who have not achieved at least a 50% improvement in EASI at week 16 compared to baseline (day 1). The randomized treatment assignments for the non-responders will remain blinded until the end of study.

In Part B, there will be no dose modification.

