### Switching Date

**If a subject is determined as non-responder at week 16 in Part A as specified by the eCRF, the Switching Date of this subject will be defined as the date that the subject takes the first dose of tezepelumab 420 mg SC Q2W after week 16 in Part A.**

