## **7.3 Final Analysis**

The final analysis will occur when the end of study date described in [Section 5.2](#) has been observed, and the data have been entered, cleaned and locked. The final analysis will analyze efficacy and safety over the entire study period for Part A and Part B. For this, Part A and Part B will be analyzed separately.

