#### 9.5.2 Analyses of Secondary Efficacy Endpoint(s)

The secondary estimands will be analyzed using **FAS – Part A**. Secondary endpoints are defined in [Section 5.6](#).

For the binary endpoint, EASI 50/90 at week 16, the treatment effect will be **analyzed** using a logistic regression model adjusting for baseline EASI. From this model, odds ratio and 95% CIs will be reported comparing each tezepelumab dose group to placebo.

The time to achieving EASI 50/75/90 response prior to switching to tezepelumab 420 mg Q2W will be summarized by Kaplan-Meier (KM) curves, the number of subjects achieving EASI 50/75/90 and the number of subjects censored will be provided at available time points. Subjects who do not achieve EASI 50/75/90 will be censored at the date when formal assessments of non-responder (as defined in protocol, that is, not achieve at least 50% improvement in EASI at week 16

compared to baseline) are recorded or end of study date, whichever is the earliest. Subjects who receive rescue medication from day 29 will be censored at the point when subjects receive rescue medication.

The treatment effect for change from baseline in SCORAD and Pruritus NRS each at week 16 will be analyzed using a **Mixed Model for Repeated Measures (MMRM)**. The model for change from baseline in SCORAD at week 16 will include visit and baseline SCORAD as covariates and an interaction term between arm and visit. The model for change from baseline in Pruritus NRS at week 16 will include visit and baseline Pruritus NRS as covariates and an interaction term between arm and visit. **AR(1) variance-covariance structure will be used.** Least square means and corresponding 95% CI will be calculated for each treatment group and for the difference between treatment groups.

Serum concentration will be summarized descriptively by treatment group for each sampling time point using the PK analysis set.

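### SAP 9.5.3.1 Part B repeats Part A's switch wording, week-16 non-responder censoring and day-29 rescue cut-off, although Part B has no switch and allows rescue earlier

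*SAP*

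**What the plan says.** **Time to EASI 50/75/90.** SAP 9.5.2 introduces the Part A analysis with "The time to achieving EASI 50/75/90 response prior to switching to tezepelumab", and SAP 9.5.3.1 repeats the paragraph for Part B: "The time to achieving EASI 50/75/90 response prior to switching to tezepelumab 420 mg Q2W will be summarized by Kaplan-Meier". The Part B censoring rule begins "Subjects who do not achieve EASI 50/75/90 will be censored at the date when formal assessments of non-responder". It takes the date on which that assessment is recorded or the end of study, whichever comes first. Non-response means less than 50% EASI improvement at week 16.

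**Switching.** Protocol 5.1 says "Non-responders in Part B will not be switched to 420 mg SC Q2W at week 18 and will remain on their initial dose", and Protocol 7.4 says "In Part B, there will be no dose modification". SAP 3.1 agrees. The SAP 5.2 definition of the switching date is limited to Part A: "If a subject is determined as non-responder at week 16 in Part A as specified by the eCRF".

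**Follow-up after week 16.** SAP 7.3 states "The final analysis will analyze efficacy and safety over the entire study period for Part A and Part B". SAP Appendix A has EASI windows at weeks 24, 36, 48, 50, 52 and 70.

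**Rescue.** SAP 9.5.3.1 Part B adds "Subjects who receive rescue medication from day 29 will be censored at the point when subjects receive rescue medication". SAP 5.4 to 5.6 use the same day 29 when deriving scores and binary endpoints for both parts. Protocol 7.1.5 bars rescue for the first 4 weeks in Part A only. For Part B, Protocol 7.1.5 and 7.1.7 open rescue after week 2, and background TCS is permitted once day 1 activities are complete.

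**The concern.** In Part A the censoring rule has a purpose: non-responders change treatment at week 18, so later EASI values no longer reflect the randomised arm. In Part B nothing changes at week 18. Censoring there on week-16 non-response removes subjects because of their outcome while they are still on assigned treatment and still being assessed. Kaplan-Meier then assumes that those removed would have responded at the same rate as those who remain.

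Day 29 likewise matches Part A's 4-week bar but not Part B's earlier rescue window, so some early rescue is never counted. The examples in SAP 5.6 also speak of TCS/TCI use without the word *rescue*. Read literally, they would score permitted background TCS in Part B as non-response.

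Time to EASI 50/75/90 is a listed Part B endpoint (SAP 2.1). What is at stake is the part of those curves after week 16 and the early binary response rates, in about 40 versus 20 subjects.

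**Working it through.** **The plan's own Part B figure.** SAP 3.2 gives a 95% CI half-width of about 20% for 40 versus 20 subjects.
- IGA 0/1, 40% v 10%: 1.96 × √(0.24/40 + 0.09/20) = 20.1 points.
- EASI 75, 50% v 15%: 1.96 × √(0.25/40 + 0.1275/20) = 22.0 points.

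The figure reproduces for IGA and is slightly low for EASI 75.

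**Censoring, EASI 75.** Let a be the share reaching EASI 75 by week 16, b the share at EASI 50 but not 75, and c the EASI 50 non-responders (a + b + c = 1). Let qb and qc be the later EASI 75 rates in b and c.
- True proportion = a + b·qb + c·qc.
- All of c censored at week 16 (plain reading): KM = a + (1 − a)·qb, so bias = c·(qb − qc).

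The values of a (15% and 50%) are the EASI response rates in SAP 3.2. The rest is assumed: b/c of 35/50% on placebo and 25/25% on tezepelumab, with qb = 30%.

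| qc | True: placebo, tezepelumab | True difference | KM: placebo, tezepelumab | KM difference |
|---|---|---|---|---|
| 0% | 25.5%, 57.5% | 32.0 | 40.5%, 65.0% | 24.5 |
| 10% | 30.5%, 60.0% | 29.5 | 40.5%, 65.0% | 24.5 |
| 20% | 35.5%, 62.5% | 27.0 | 40.5%, 65.0% | 24.5 |
| 30% | 40.5%, 65.0% | 24.5 | 40.5%, 65.0% | 24.5 |

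A second assumed set has b/c of 15/70% on placebo and 15/35% on tezepelumab, with qb = 50% and qc = 10%. The bias is 0.70 × 0.40 = 28 points on placebo and 0.35 × 0.40 = 14 on tezepelumab. The difference is then 17.5 against a true 31.5.

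**Direction.** Both sets use the same later rates in each arm. Keep the first set's shares but let qb/qc be 50/10% on tezepelumab and 20/10% on placebo. KM gives 75% v 32% (43 points) against a true 65% v 27% (38 points). Here the difference widens.

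**Alternative reading.** Suppose only subjects who never achieve the response are censored at week 16. Then KM = 1 − (1 − a)·b·(1 − qb)/(b + c·qc). With the first set and qb = qc = 30%, this gives 58.4% v 73.1% (difference 14.7) against a true 40.5% v 65.0% (24.5).

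**EASI 50.** A subject assessed at week 16 who has not yet reached EASI 50 is by definition a non-responder. On the plain reading essentially everyone still at risk is censored and the curve stops at week 16. On the alternative reading it climbs to 100%. For example, with 10 of 20 responding by week 16 and 1 to 3 later, the true figure is 55% to 65%.

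**Rescue cut-off.** Target day = 7 × week + 1, so week 2 is day 15, week 4 day 29 and week 16 day 113. If Part B rescue opens at day 15, days 15 to 28 (14 days) go uncounted: 14 of 15 permitted days up to week 4, 14 of 29 up to week 6, 14 of 71 up to week 12, and 14 of 99 up to week 16. The ±3-day visit window at week 2 makes it 11 to 17 days.

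For scale at week 16, start from IGA 0/1 of 16/40 v 2/20 (30 points, OR 6.0). One rescued placebo subject counted as a responder gives 16/40 v 3/20 (25 points, OR 3.8). One on tezepelumab gives 17/40 v 2/20 (32.5 points, OR 6.7). Both shifts are small beside the 20-point half-width.

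**The case against.** **The bias may never arise.** The SAP describes an eCRF non-responder determination only for Part A. If none exists in Part B, censoring falls to the end of study and only stray words are left. This stands, and a reader should not infer that the Part B curves are certainly biased. But the rule is written into the Part B text with its definition spelled out, and that definition needs only baseline and week-16 EASI. One programmer could derive it and another not, and they would produce different curves.

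**Little depends on it.** The planned Part B look at week 16 is unaffected by this censoring. Long-term response is also analysed as binary endpoints at weeks 24, 36 and 52, and Part B tests no hypotheses. This stands and limits the importance of the point.

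**A shrinking treatment difference.** A reader might infer this from the larger placebo bias in the table. It follows only if later response rates are equal in both arms. The documents give no such rates, and the 43 v 38 point example goes the other way.

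**Days are not subjects.** The 14-of-15 count is calendar time, not a share of rescued subjects. Rescue begun before day 29 and continued past it would plausibly be caught. Protocol 7.1.5 also describes higher-potency TCS as rescue in Part B without a week-2 limit, so the 14-day count rests on one reading of that section.

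**Censoring at rescue versus scoring it as non-response.** A reader might call this contrast between the Kaplan-Meier text and the binary endpoints an error. The documents do not support that. SAP 9.5.2 does the same in Part A, and SAP 5.4 disregards EASI scores after rescue, which fits censoring. It is an estimand choice for both parts.

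**Conclusion.** The Part B time-to-EASI rules do not fit the Part B design and should be corrected. The reference to switching is wrong without conditions.

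The bias is conditional on a week-16 non-responder assessment being recorded or derived in Part B. If it is, on the plain reading the EASI 50 curve ends at week 16, and the EASI 75/90 curves are too high after it unless partial responders and non-responders later respond equally. In the two illustrations with common later rates, the EASI 75 excess runs from 0 to 28 points on placebo and 0 to 14 on tezepelumab. These sizes rest on assumed week-16 shares and late-response rates, and the effect on the arm difference has no fixed sign.

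The day-29 rescue cut-off is a separate mismatch. It matters mainly at week 4 and is probably small at week 16. The literal wording of the SAP 5.6 examples could matter more, because it would reach permitted background TCS, but the documents give no TCS usage rates from which to size it.

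No alpha, power or Part A conclusion changes.

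**What to change.** 1. In SAP 9.5.3.1 Part B, delete the reference to switching and the censoring at the non-responder assessment. Censor non-achievers at their last EASI assessment.
2. Reconcile the statements in Protocol 7.1.5 and 7.1.7 on when TCS use counts as rescue in Part B and from when. Then, for Part B in SAP 5.4 to 5.6 and 9.5.3.1, replace day 29 with the start of Part B rescue as the reconciled protocol gives it.
3. Insert the word *rescue* in the SAP 5.6 examples, and state how rescue TCS is told apart from background TCS in the collected data.

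The first change costs a wording edit and minor programming, since the later EASI windows already exist. For the other two, Protocol 7.8.2 already provides for therapy name, indication, dose and start and stop dates, but the documents show no field that marks TCS as rescue. The sponsor should therefore confirm that the existing records can make the distinction.

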#### **9.6 Safety Analyses**

The safety analyses will be performed separately for Part A and Part B. Furthermore, the safety analyses for Part A will be performed in two different periods considering that the switching of 420mg Q2W is scheduled on week 18 for EASI 50 non-responders.

- **Day 1 to week 16 for all subjects in Safety Analysis Set – Part A.**
  - For non-switchers, search window stops at 1 day before the next dosing date after week 16 dose, or end of safety follow up
  - For switchers, search window stops at 1 day before switching to 420mg Q2W
- **Day 1 to EOS, for all subjects in Safety Analysis Set – Part A. For subjects in the Switcher Analysis Set, the actual treatment received is the combination of the actual treatment they received before switch and tezepelumab 420 mg.**

The safety analyses will be performed by actual treatment received (defined in [Section 5.1](#)).

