7.1.5 Other Treatment Procedures

During the 28-day screening period, subjects must discontinue from all AD therapies, except for approved moisturizers (see [Section 7.1.7](#)), for at least the 7 consecutive days immediately prior to day 1. During the study, approved moisturizers are allowed to be applied, with the exception of 8 hours prior to any scheduled visit.

Medications and procedures permitted at any time during the study for subjects enrolled in Part A and Part B include:

- Basic skin care (cleansing and bathing), emollients, bleach baths, topical anesthetics, and antihistamines (all for any duration)
- Medications used to treat chronic diseases such as diabetes, hypertension, and asthma

Part A

In Part A of the study, if needed to control intolerable AD symptoms, rescue treatment for AD may be provided at the discretion of the investigator. Rescue is not allowed in the first 4 weeks of Part A. Topical calcineurin inhibitors may be used for rescue, but are to be reserved for problem areas only (eg, face, neck, intertriginous and genital areas). Investigators are to attempt to limit the first step of rescue therapy to topical medications, and escalate to systemic medications only for subjects who do not respond adequately following at least 7 days of topical treatment. If a subject receives rescue treatment with systemic corticosteroids or nonsteroidal systemic immunosuppressive drugs

(eg, cyclosporine, mycophenolate-mofetil, azathioprine), study treatment is to be immediately discontinued.

All subjects are to complete the schedule of study visits and assessments whether or not they complete study treatment or receive rescue treatment for AD.

Part A Rescue Guidance

Subjects who use TCS are to apply medium potency TCS once daily to areas with active lesions. Low potency TCS should be used once daily on areas of thin skin (eg, face, neck, intertriginous, genital areas, areas of skin atrophy) or for areas where continued treatment with medium potency TCS is considered unsafe.

Triamcinolone acetonide 0.1% cream or fluocinolone acetonide 0.025% ointment are recommended as medium potency TCS therapy; hydrocortisone 1% cream is recommended as low potency TCS therapy. After lesions are under control (clear or almost clear), subjects are to switch from medium potency to low potency TCS and treat once daily for 7 days, then cease TCS therapy.

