#### Actual treatment received

##### *Part A:*

For Part A of the study, actual treatment will be defined as follows:

- If a subject either a) did not need to switch to tezepelumab 420 mg during the study, or b) should have switched to tezepelumab 420 mg but did not successfully do so, then the subject is considered a non-switcher. The subject's actual treatment received is defined below:
  - from day 1 until EOS for safety analysis of Day 1 to EOS (For safety analysis of Day 1 to week 16, use from day 1 until the day before the next dosing date after week 16 dose),
    - If a subject receives placebo only, the actual treatment will be defined as placebo
    - If a subject receives two or more doses of tezepelumab, the actual treatment will be defined as the highest dose of tezepelumab the subject receives since the date of the second IP (inclusive)
    - If a subject receives only one dose of tezepelumab, the actual treatment will be defined as the dose of tezepelumab the subject receives
- If a subject should have switched to tezepelumab 420 mg during the study and received a switching dose, then,
  - From day 1 until the day before the switch,
    - If a subject receives placebo only throughout this period, the actual treatment will be defined as placebo
    - If a subject receives two or more doses of tezepelumab during this period, the actual treatment will be defined as the highest dose of tezepelumab the subject receives since the date of the second IP (inclusive) until the day prior to the switch
    - If a subject receives only one dose of tezepelumab during this period, the actual treatment will be defined as the dose of tezepelumab the subject receives
  - From the date of switch until EOS,
    - If a subject receives at least one dose of tezepelumab 420 mg during this period, the actual treatment will be defined as tezepelumab 420 mg

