**Part B:**

**For Part B of this study, the actual treatment will be defined as follows:**

- **If a subject receives placebo throughout the Part B of this study, the actual treatment will be defined as placebo**
- **If a subject receives at least one dose of tezepelumab in Part B of this study, the actual treatment will be defined as the highest dose of tezepelumab the subject receives**

Treatment-Emergent Adverse Events

Events categorized as Adverse Events (AEs) including events reported as **Disease Related Events** starting on or after first dose of investigational product as determined by **“Did event start before first dose of investigational product” equal to “No” or missing on the Events eCRF (including either “adverse event” or “disease related event” record on eCRF) and up to End of Study Date.**

Disease Related Events

**Disease-related events are events (serious or non-serious) anticipated to occur in the study population due to the underlying disease as recorded on the Events eCRF page. Details on disease related events can be found in protocol Appendix 4.**

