**5.2 Study Dates/Timelines**

End of Study (EOS) Date

The End of Study Date for a **subject** is the date **the subject completes the safety follow-up, or the date of the Early Termination (ET) visit if no safety follow-up is completed. The date the subject has ended the study is recorded on the End of Study Electronic Case Report Form (eCRF).**

Primary Completion Date

The primary completion date is the date when the last subject has completed the assessments for week 16 in Part A of the study.

If the study concludes prior to the primary completion date originally planned in the protocol (ie, early termination of the study), then the primary completion date will be the date when the last subject is assessed or receives an intervention for evaluation in the study (ie, last subject last visit).

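### The Part A Day 1 to week 16 safety window has no week-16 stop for subjects with no dose after the week 16 dose, so observation time depends on stopping treatment

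*SAP*

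**What the plan says.** SAP 9.6 splits Part A safety into two periods. The first is labelled "Day 1 to week 16 for all subjects in Safety Analysis Set – Part A". Its end depends on dosing:

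- Non-switchers: "For non-switchers, search window stops at 1 day before the next dosing date after week 16 dose, or end of safety follow up".
- Switchers: "For switchers, search window stops at 1 day before switching to 420mg Q2W".

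SAP 5.1 describes the same period when it defines actual treatment, but gives only the dosing-date cut: "For safety analysis of Day 1 to week 16, use from day 1 until the day before the next dosing date after week 16 dose". It also places in the non-switcher group anyone who "should have switched to tezepelumab 420 mg but did not successfully do so, then the subject is considered a non-switcher".

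Nothing else in the SAP closes the window earlier. The treatment-emergent definition in SAP 5.1 runs "and up to End of Study Date". SAP 5.2 sets a subject's end of study as the date "the subject completes the safety follow-up, or the date of the Early Termination (ET) visit if no safety follow-up is completed".

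SAP 9.6.1 summarises events by subject incidence. Exposure-adjusted rates are planned only for day 1 to week 52, in the final analysis. SAP 7.2 gives the aim of the primary analysis as safety and efficacy through week 16.

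**The concern.** A window that closes at the next dose works only for subjects who have a next dose. Without one, the dosing-date stop does not exist, and only the end of safety follow-up remains. Reading the rule as whichever comes first does not help, because one of the two dates is absent. This covers subjects who stop before week 16 and subjects whose last dose is the week 16 dose. A subject who misses week 16 but is dosed at week 18 has no clearly defined cut.

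The length of observation therefore depends on a post-randomisation event. Stopping could plausibly differ by group: Protocol 7.1.5 and 7.4.2.1 have study treatment discontinued after systemic rescue, so poor disease control can lead to stopping, and disease control is what the groups are expected to differ on. SAP 5.1 also counts disease-related events among treatment-emergent events, so the outcome is linked to the reason for stopping.

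What is at stake is the comparison with placebo before non-responders switch. The later period, Day 1 to end of study, mixes in switchers and is no substitute.

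**Working it through.** **1. The plan's own follow-up figure.** SAP Appendix A sets the target day as week × 7 + 1. The last scheduled dose is at week 50, and 50 + 20 = week 70. End of treatment is at week 52, and 52 + 18 = week 70. Target day: 70 × 7 + 1 = 491. The documents agree here.

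**2. Window lengths.**

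- Dosed on schedule at week 18: target day 18 × 7 + 1 = 127, so the window closes on day 126.
- No later dose, follow-up ending 20 weeks after the last dose (Protocol 9.1.3, 9.2.3.1): last dose day 1 gives 20 × 7 + 1 = day 141; week 14 gives 34 × 7 + 1 = day 239; week 16 gives 36 × 7 + 1 = day 253. Against 126 days these are ratios of 1.1, 1.9 and 2.0.
- No later dose, kept on the visit schedule (Protocol 7.1.5: "All subjects are to complete the schedule of study visits and assessments whether or not they complete study treatment"): day 491, a ratio of 3.9.

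**3. Illustrative effect on crude incidence.** The only related planning figure is a 10% dropout rate, not split by arm (SAP 3.2). All inputs here are assumptions: 5% stopping in one group and 20% in another, no true difference, constant hazard λ. With stopping share d, incidence I18 over the regular 18-week window and incidence S among stoppers:

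Group incidence = (1 − d) × I18 + d × S, where S = 1 − exp(−λT)

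Gap = (0.20 − 0.05) × (S − I18) = 0.15 × (S − I18)

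| Assumed incidence | I18 | S, shorter follow-up | S, to week 70 | Gap, shorter | Gap, week 70 |
|---|---|---|---|---|---|
| 5% by week 18 | 0.050 | 0.074 | 0.181 | 0.4 points | 2.0 points |
| 20% by week 18 | 0.200 | 0.285 | 0.581 | 1.3 | 5.7 |
| 50% by week 18 | 0.500 | 0.643 | 0.933 | 2.1 | 6.5 |
| 30% by week 16 | 0.331 | 0.464 | 0.790 | 2.0 | 6.9 |
| 50% by week 16 | 0.541 | 0.703 | 0.952 | 2.4 | 6.2 |

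In the first three rows, shorter follow-up means 20 weeks after a last dose spread evenly over weeks 0 to 14 (mean window 190 days). In the last two rows it means follow-up ending at week 28. Excluding the rare-event row, the ranges are 1.3 to 2.4 and 5.7 to 6.9 points. With about 60 subjects per group, that is 0.8 to 1.4 and 3.4 to 4.1 subjects.

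**4. Sensitivity, 20% by week 18.**

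- Hazard halves from 14 days after the last dose: S = 0.199 (20-week follow-up) or 0.387 (week 70). The gaps become about 0.0 and 0.15 × (0.387 − 0.200) = 2.8 points.
- Stoppers leave at the early termination visit, 14 days after the last dose, with no safety follow-up: S = 0.106. The gap is 0.15 × (0.106 − 0.200) = −1.4 points (18.1% versus 19.5%).
- Common stop at day 126, constant hazard, stoppers followed to that day: both groups show 20.0%.

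**The case against.** Following stoppers off drug is a defensible safety choice. The table is descriptive, with no hypothesis test. SAP 9.2 tabulates discontinuation of investigational product with reasons by group, so an imbalance would be visible, and exposure-adjusted rates come at the final analysis. With the shorter follow-up the distortion is only about one subject per group. All of that stands as a limit on size. It does not remove the defect: the disposition table reveals unequal stopping but does not correct incidences, the exposure-adjusted rates cover a different period, and a table labelled to week 16 should not include events from well beyond it.

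Three stronger readings are tempting, and the documents do not support them.

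- *Every stopper is searched to week 70.* Protocol 7.1.5 supports long follow-up, and 9.2.3.1.1.2 collects adverse events through end of study. But 9.1.3 places the follow-up visit 20 weeks after the final dose, 9.2.3.1 offers the same limit as an alternative end of collection, and 9.2.3.1.1.3 requires serious adverse event reporting only for 20 weeks after the last administration. Day 491 is an upper limit.
- *Groups with more stopping must show extra events.* Under SAP 5.2, a subject who completes no safety follow-up ends at the early termination visit. That window can be shorter than the regular one, and the sign can reverse.
- *This is a strictly randomised comparison.* SAP 9.6 analyses safety by actual treatment received.

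**Conclusion.** The rule is wrong as written. Applied exactly, it gives subjects with no later dose a window that contradicts the period's label, the through-week-16 aim in SAP 7.2 and the description in SAP 5.1. Crude incidences can then be biased between groups if stopping differs.

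That part rests on the text alone. The size does not: it depends on stopping and event rates that the documents do not give. Under the stated assumptions the gap is about 1.3 to 2.4 points with the shorter follow-up and 5.7 to 6.9 points at the week-70 limit. It is less for rare events or if the hazard falls after stopping, and it may reverse if many subjects end the study at the early termination visit. At the primary lock only follow-up accrued so far can count, so the extra time also depends on when a subject enrolled, and the full effect may not yet show. If stopping is equal across groups, the incidences are still mislabelled, but under the equal constant-hazard assumption the window alone creates no gap between groups.

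**What to change.** In SAP 9.6, end the Day 1 to week 16 window for every subject at the earliest applicable of:

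- (a) the day before the first dose following the week 16 dose, which for switchers is the switching dose;
- (b) for subjects with no such dose, a fixed day such as Study Day 126, the day before the week 18 target day 127;
- (c) the End of Study Date.

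Identify the dose in (a) by its scheduled visit, so that a missed week 16 dose does not leave the cut undefined. Restricting the fixed day to subjects with no later dose matters because Protocol 7.6 allows dosing within 1 week of target: a week 18 dose may fall on day 134, and a universal day-126 cap would drop days 127 to 133. Make SAP 5.1 match.

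The cost is a small edit in two SAP sections, with no change to data collection. A few later events leave this table but stay in the Day 1 to end-of-study tables. Windows shortened by early exit remain shorter; adding exposure-adjusted rates for this period would address that.
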